## V. Physical Activity Goal

All participants will receive an enhanced physical activity monitor treatment, which includes goal setting with a physical activity prescription, and self-monitoring with a physical activity monitor. We will follow the physical activity prescription guidelines that were successfully used in our prior work. First, steps walked per week and per day (step counts) are obtained from the Fitbit, which is distributed during initial eligibility screening and worn for one week prior to the start of the intervention. The baseline step count per day is identified by averaging daily step counts over at least four days of valid data. Based on previously published step count data, counts per day have been classified as: < 5,000 = "sedentary"; 5,000-7,499 steps = "low active"; 7,500-9,999 steps = "somewhat active"; 10,000-12,499 steps = "active"; and  $\geq 12,500$  steps = "high active". Adults in the U.S. take an average of 5,117 steps per day. Adding 3,000 steps to 5,117 steps per day would move an individual from the "low active" into the "somewhat active" category. Thus, each participant is given an overall goal to increase her steps above her baseline by a minimum of 3,000 steps per day, an increase that approximates 30 minutes of physical activity at a moderate walking pace.

To enhance self-efficacy, the research team will work with each woman to set an initial physical activity goal to gradually increase walking frequency, duration, and intensity. Gradually increasing frequency, duration, and intensity of physical activity promotes physical activity adherence and reduces risks of musculoskeletal injury and adverse cardiac events. Participants may elect to only increase frequency without moving to increased duration and intensity. Thus, for activity progression, the research team will first emphasize frequency (walking more times throughout the day), then duration (walking for longer periods of time), and finally intensity (walking at a faster pace). Walking is initiated by beginning with incremental increases in routine/unplanned physical activity throughout the day. Participants will be given an initial goal of walking 600 steps/day over their baseline mean, by 8 weeks, to increase their frequency of walking.

Depending on participant preferences, for participants who reach the "somewhat active" classification through their routine physical activity, they may begin structured physical activity (e.g., leisure-time walking), continue to increase their routine physical activity with a focus on walking for longer periods of time, or combine both strategies as additional sources of steps. The "somewhat active" classification was selected as the point to introduce structured/planned leisure physical activity because the "active" classification is associated with intentional (structured) activities. Thus, participants in the "somewhat active" classification who choose to add structured bouts of walking may gradually increase over four weeks structured activity to a

duration of 30 minutes, frequency of three to four times per week, consistent with American College of Sports Medicine. Participants who are able to reach the “active” classification should have the conditioning to assume moderate-intensity walking, per American College of Sports Medicine recommendations, either during 30 minutes of planned walking or physical activity bouts of  $\geq 10$  minutes. Participants at this level are encouraged to walk faster.

The initial step count goal will be entered electronically into a Fitbit, a slim wristband physical activity monitor to be worn at all times except during bathing and swimming, through a Fitbit application on a mobile device using the Fitbit.com website. The physical activity monitor allows participants to self-monitor their walking steps, distance, and intensity. Participants automatically receive notifications in relation to their PA as follows: The Fitbit PA monitor gently vibrates to notify the participant when she has achieved 100% of her daily step goals. Also, the Fitbit mobile app generates an automatic notification in the form of a friendly message, when a participant has achieved 75%, 100% or 125% of her daily step goal provided that the Fitbit mobile app is on or actively running in the background.

Fitbit data will be collected using the iCardia application and be presented on a virtual dashboard. The dashboard will show the research team real time participant physical activity data. These data will be used to provide suggested physical activity step goals at the end of the early adoption (Week 8) and late adoption (Week 34) phases. The iCardia application will be used to send text-messages based on the incoming physical activity data.

Text message reminders are sent to all of the participants every Monday to remind them to sync their Fitbit. If the participant has not synced their Fitbit in 7 days, they receive a phone call. Participants will receive another phone call two days after that if they still have not synced their Fitbit. For the participants in the text message group, in addition to the Monday sync message, they receive an additional message later on Monday to sync if they have not already done so, and receive an additional text message to sync on Tuesday morning, if they still have not synced their Fitbit. The text message group is then given a step classification text message on Monday for those that have synced, and Tuesday afternoon for all remaining participants in this group, irrespective if they have synced or not. During Weeks 35-50 (maintenance), all participants will only be sent one text message weekly, and that will be a reminder every Monday to remind them to sync their Fitbit.

The research team will create anonymous email and Fitbit accounts for all participants enrolled in the study. To ensure privacy and confidentiality, we will use unique Subject ID codes for the creation of online accounts. No personal or private identifiers will be stored in the Fitbit servers at any point in time. This account will be used only for the purpose of this study, where the email address will be used to communicate information about Fitbit data to the research team.

All participants will have a program orientation, which will include guidance on setting a physical activity goal and using their physical activity monitor, as well as viewing a video that will give information related to self-monitoring their steps, and proper walking and stretching techniques.

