### *Initial Eligibility Screening*

- Interested participants will be asked to provide verbal consent to be screened for inclusion criteria (listed again below)
  - Rush University Medical Center female employee
  - Age 18 to 70
  - Speak and read English language
  - Have a Smartphone with a text messaging plan and assess if potentially compatible with a Fitbit
  - Provide information about their current physical activity

- Interested participants will be requested to provide the research team with information about how they heard about the study
- Those who meet these criteria will be scheduled for their next visit where they will be consented and further screened
- Those who need to supply additional information regarding their smartphone will be contacted within one week to determine the compatibility of their device with study procedures
- Those who do not meet these criteria will be thanked for their time and considered ineligible for participation

*Consent and Health Screening Appointment*

- Because of changes related to COVID-19, participants will be asked to review an emailed consent ahead of time, prior to signing the consent at the in-person visit.
- The consent process will be completed in a private room in the Rush University Medical Center, and will include the Study Consent and the consent for Photographing and Videotaping
- Following the consent process, should a participant choose to continue their participation they will be entitled to continue directly into the screening visit, or schedule an additional appointment for those such procedures
- Screening includes:
  - Completing the Physical Activity Readiness Questionnaire (PAR-Q & You)
  - Completing the Health History questionnaire
    - Includes questions about health history, health problems, gynecological health, and psychosocial health
  - Undergoing height, weight and waist measurements
  - Undergoing three blood pressure (B/P) readings
  - Being asked for A1C results done within the past 30 days
    - If they do not remember or do not have test results, they will be provided with A1C testing using self-monitoring kits to determine their A1C level for screening, at no cost to them (using a A1CNow + monitor which is approved by the FDA for self-monitoring of A1C)

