  - Participants that are identified to have had issues with the monitors (e.g. they were not using them as instructed) will be asked to wear them for an additional week of wear time to re-evaluate their eligibility
  - Participants that are screened eligible based on their step count data will be contacted for scheduling their Baseline Interview

*Baseline Interview and Randomization (D1)*

- Because of changes related to COVID-19, participants will complete the D1 questionnaire online using a secure REDCap survey link
- D1 data collection will include the following:
  - Questionnaire completion:
    - Demographics (age, ethnicity, marital status, children, caregiver status, education, income/hardship, job, shift)
    - Neighborhood Environment Walkability Scale (NEWS)
      - 28 items assessing respondent's perceptions of characteristics in their neighborhood that are conducive to walking
    - Exercise Benefits/Barriers Scale (Revised for PA)
      - 43 items about statements that relate to positive/negative PA ideas
    - McAuley's Self-Efficacy for Overcoming Barriers to PA
      - 17 items reflecting beliefs in ability to continue to be physically active in the face of barriers
    - Social Support and Exercise (Revised for PA)
      - 13 items assessing scale of family and friend support
    - Outcome expectations
      - 11 items measuring expected change due to becoming more physically active
    - International Physical Activity Questionnaire (IPAQ) long-form
      - 27 items assessing days per week and hours/minutes per day of sitting, occupational, light, moderate, and vigorous leisure-time PA
    - Sedentary Behavior:
      - Time spent sitting participating in 9 sitting behaviors in past 7 days resulting in total minutes per week of sedentary behavior

- Emotional Distress-Depression Short Form 8b
  - 8 items measuring depressive symptoms over the past 7 days
- PROMIS Scale v 1.2
  - 10 items assessing general health, PA, emotional problems, and fatigue
- PROMIS Sleep Impact Short Form
  - 10 items, assessing past 7 days of sleep
- Participants will be asked to sign an Oath of Confidentiality agreement that notes that they will not discuss their experience with the physical activity program with anyone else in their workplace until after the participation in the study ends.
- Participants will be thanked for their time, and will schedule their program orientation appointment to occur within a target two-week window.

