- Participants will be randomly assigned to one of the first two initial treatments (physical activity monitor, or physical activity monitor+text message)
  - See section **IX. Randomization** for further details on the randomization process

*Program Orientation Appointment*

- Because of changes related to COVID-19, the Program Orientation Appointment will now be done using Zoom or Webex
- All participants will be asked to have their Fitbit available for this appointment, and will be provided guidance on general device usage throughout the study
  - Participants will be asked to refer to their Physical Activity Manual for information about the Fitbit and about walking
  - Participants will be asked to wear their Fitbit when they are awake, preferably all of the time they are awake
  - Participants will be instructed on how to review their daily and weekly steps on their Fitbit
- Participants will be provided guidance on setting their physical activity goal (See Section **V. Physical Activity Goal** for more details)
- All participants will be shown an instructional video related to walking, proper stretching, and using a Fitbit
  - All participants will be reminded that they can contact research team members during the study with any questions or concerns
- A research team member will complete a Behavioral Competencies Checklist, documenting that the participant can demonstrate skills correctly regarding the Fitbit Charge 2 and setting their Step Goal
- Participants who have been assigned to the physical activity monitor+text message initial treatment will also receive the following:
  - Instructions on what to expect regarding receiving text messages
  - A brief motivational interviewing session to identify motivational text messaging strategies to overcome their perceived barriers to increasing their daily steps
    - During this session, participants will suggest their own text messages and have the opportunity to select from an existing physical activity text messaging database
- Monitoring of physical activity will start immediately after completion of the program orientation. Evaluation of response/non-response for each participant will take place 8 weeks after the orientation date.

- Participants will be reminded that the research team will remotely monitor their progress to ensure the following:
  - Adequate wear-time of the device
  - Proper syncing of data between Fitbit and iCardia

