  - 21 items measuring satisfaction with the Fitbit Process
- Physical Activity Text Messaging Satisfaction Tool
  - 4 items measuring satisfaction with the text messaging intervention component
- Participants will be asked to come to the Physical Activity lab for a brief appointment to obtain:
  - Physical measures including:
    - Three blood pressure readings, pulse, weight and waist circumference (a Physical Measures handout will be given to the participant that records these findings)
  - Fitness assessment:
    - Step fitness test
- The research team will give the participant a new step goal, based on their average daily step count (See **V. Physical Activity Goal** for more information about goal adjustment)
- For the second time in the study, participants will be given an Actigraph to wear for one week along with instructions for use
  - Participants will be instructed to continue to wear their Fitbit monitor every day
    - Participants will only be wearing both monitors, the Actigraph and the Fitbit, simultaneously for one week during the prescribed Actigraph wear time
- Arrangements will be made by the research team staff to pick up participants' physical activity monitors one week later, or participants will have the option of returning their monitors to the College of Nursing using a secured metal drop-box on the outside of the main office door
- If a participant has been randomly assigned to receive the augmented Personal Calls Component of the study (See **VII. Personal Calls Component** for more information):
  - The research team will explain to the participant that they will be receiving five brief motivational interviewing telephone calls made by an interventionist
    - The research team will arrange a schedule for the participant to receive personal calls every two to three weeks over the upcoming 24 weeks
- If a participant has been randomly assigned to receive the augmented Group Meeting Component of the study (See **VIII. Group Meeting Component** for more information):
  - The research team will explain to the participant that they will be participating in five, 45-60 minute group meetings held every 4-6 weeks over the next 6 months

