## VII. Personal Call Component

Motivational personal calls will be based on the model consisting of five brief (approximately 10 minute) Motivational Interviewing telephone calls, made by an interventionist, every two weeks during the first 10 weeks of late adoption, and five calls every three weeks for the following 14 weeks (total 10 personal calls in late adoption Weeks 11-34). Participants will be given feedback based on their step counts in the prior week in relation to their goal (obtained from iCardia). The interventionist, who will be trained in Motivational Interviewing methods/techniques, will explore the participant's feelings toward behavior change, assist in articulating self-efficacy in overcoming problems/barriers to physical activity, identify benefits of physical activity, and assist in developing a plan to increase physical activity. Using Motivational Interviewing, the interventionist will tailor the discussion to match the participant's needs, experiences, barriers, motivation, and confidence. Suggestions for addressing problems will only be provided after the participant has explored options and agreed to receive feedback. The interventionist will follow a semi-structured protocol that provides the basic flow of each call, allowing for discussion and reflective listening. The calls will emphasize how the participant can overcome barriers to obtain goal steps.

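### No visit after screening is described as asking about injury or cardiac events, although the protocol names both as risks, and the SAP plans no harms summary

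*Protocol*

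**What the plan says.** Protocol Section V names the two risks when it explains why activity is raised step by step: "Gradually increasing frequency, duration, and intensity of physical activity promotes physical activity adherence and reduces risks of musculoskeletal injury and adverse cardiac events". This is the only mention of adverse events in either document.

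Health problems are asked about before randomisation. At the consent and health screening appointment (Section IV) women complete the PAR-Q & You and a Health History questionnaire, described so: "Includes questions about health history, health problems, gynecological health, and psychosocial health". Neither is listed again at D1 to D4.

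The later visits are itemised closely. The nearest repeated health instrument is the PROMIS scale, described as "10 items assessing general health, PA, emotional problems, and fatigue". The lab measures at D2, D3 and D4 are "Three blood pressure readings, pulse, weight and waist circumference", plus a step fitness test.

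For problems between visits, the Program Orientation text gives an open line: "All participants will be reminded that they can contact research team members during the study with any questions or concerns". Section V adds a phone call after seven days without a sync, and another two days later if there is still none.

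Scheduled contact between D2 and D3 depends on condition. Section VII gives the personal-call arm a "total 10 personal calls in late adoption Weeks 11-34", whereas the D2 visit text tells participants to expect five. Section VIII provides five group meetings. Responders simply continue their initial treatment. In maintenance, the only text message is the sync reminder: "all participants will only be sent one text message weekly, and that will be a reminder every Monday to remind them to sync their Fitbit".

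In the SAP, efficacy, mediation and moderation, and cost-effectiveness are covered. It has no harms section.

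**The concern.** The plan treats exertional risk as real. It screens for it, and it admits women with a positive PAR-Q or with diabetes only after their own provider clears them. It then asks each woman to add at least 3,000 steps a day in the long run, starting with 600. After that, no listed instrument is described as asking whether she was hurt, had cardiac symptoms or needed medical care.

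Two things are at stake. First, what the team learns about harms between visits depends partly on how often and in what setting it talks to each woman, and that is set by treatment condition. A count of harms by arm from such information would mix true risk with opportunity to mention it. Second, responder status rests on Fitbit steps in weeks 6-8. A woman who was injured or ill then may miss the 600-step criterion, be classed as a non-responder and be randomised to an added treatment, with no planned data item to show why her steps were low.

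**Working it through.** The documents give no event rate and no harms analysis, so there is no stated figure to reproduce. The check is a reading of the visit lists and a count of contacts.

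**Step 1: is the question asked anywhere after screening?**
- D1 to D4 questionnaires: benefits and barriers, self-efficacy, social support, outcome expectations or realizations, IPAQ, sedentary behaviour, depression, PROMIS, sleep, and, at later visits, satisfaction, social provisions and diffusion tools. None is described as recording injury, falls, cardiac symptoms or medical care.
- D2 to D4 lab measures: blood pressure and pulse could reveal an abnormal reading. They do not record an injury or a past event.
- Remote data: Section V gives staff real-time activity data, so a fall in steps can be seen. No section says that a fall prompts an enquiry or that its reason is recorded.
- Protocol Sections I to XII run without a gap and include no adverse-event definition, form or reporting section.

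**Step 2: contact common to all women.** The D2, D3 and D4 lab visits, new step goals at D2 and D3, the missed-sync calls and the open contact line.

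**Step 3: scheduled contact between D2 and D3 that differs.** Call length (about 10 minutes) is from Section VII; meeting length (45-60 minutes) is from Section VIII.

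| Condition | Contacts | Minutes |
|---|---|---|
| Personal calls, Section VII | 10 | 10 × 10 = 100 |
| Personal calls, D2 text | 5 | 5 × 10 = 50 |
| Group meetings | 5 | 5 × 45 = 225 to 5 × 60 = 300, shared with the group |
| Responders | 0 | 0 |

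Calls against meetings by count: 10/5 = 2 or 5/5 = 1. By minutes: 100/300 = 0.33 to 100/225 = 0.44, or 50/300 = 0.17 to 50/225 = 0.22. Counting contacts, calls offer the same or more opportunity; counting minutes, they offer less. Calls are also private, while meetings are discussions among co-workers. The direction of any difference between these two arms therefore cannot be read from the documents. Against responders, both augmented arms have more scheduled conversation.

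**Step 4: length of the gaps.** From D2 to D3, 35 − 10 = 25 weeks; from D3 to D4, 51 − 36 = 15 weeks. The second gap is the same for everyone.

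**Step 5: effect on Aim 1.** Aim 1 compares calls with meetings among non-responders. Section XI randomises them 1:1, stratified by initial condition. Women injured or ill in weeks 6-8 are therefore balanced between the two arms in expectation. The comparison is not biased; only the make-up of the non-responder group is unknown.

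**The case against.** The fair case against is that the point argues from silence. A separate safety plan or the consent form may cover it, and neither is in these documents. The Section V sentence is a rationale for gradual progression and promises no monitoring. No aim makes a comparative safety claim, and the intervention is walking after screening. All of that stands and limits the weight of the point. It does not supply the missing question, and harms that were never asked about cannot be recovered at analysis.

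Three stronger readings are tempting and should be resisted.

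- A reader might infer that harms can surface only if a woman contacts the team. The documents do not support this: every woman meets staff at D2, D3 and D4, is phoned if she stops syncing, and has activity data visible to staff.
- A reader might put a size on the unevenness by assuming a chance of mention per contact. At an assumed 10%, 10 calls give 1 − 0.9^10 = 0.65 and five meetings 1 − 0.9^5 = 0.41, a ratio of about 1.6, with zero for responders. None of this holds up. The 10% has no source. Counting D3 as one more contact gives 1 − 0.9^11 = 0.69 against 1 − 0.9^6 = 0.47, about 1.5, and 0.10 for responders. With five calls the ratio is 1.0. Treating a 10-minute call and a 45-60 minute meeting as equal is a further assumption.
- A reader might infer that injuries in weeks 6-8 bias Aim 1. The second randomisation rules this out, and the documents give no frequency for such injuries.

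**Conclusion.** The point holds as a gap in data collection and reporting. After screening, no visit is described as asking about the risks the protocol names, and the SAP has no harms summary. Scheduled contact between D2 and D3 ranges from none (responders) to five meetings or five to 10 calls, so harms noticed between visits would be ascertained unevenly. The size of that unevenness is not determined by the documents and, between calls and meetings, neither is its direction. The efficacy comparison in Aim 1 is unaffected. What the trial could not do is describe harms soundly by arm, or say how many non-responders were injured or ill in weeks 6-8.

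This rests on the documents being complete on the matter. If a separate safety plan exists, the protocol should cite it and the point narrows to the missing harms table.

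**What to change.** - **Collect.** Add one identical, dated item set to the online D2, D3 and D4 questionnaires for every woman: injury or fall, cardiac symptoms, medical visit or hospital stay, and illness or injury that limited walking. At D2, ask specifically about weeks 6-8.
- **Order.** Have the D2 items answered before the augmented assignment is disclosed. The D2 visit text lists notification within that visit, while Section XI places it after D2 and after the Actigraph is returned; these must be reconciled.
- **Route.** Send positive answers to an existing study role. Any care that follows is for the investigator to decide.
- **Report.** Add to the SAP a descriptive table by randomised treatment showing solicited events, volunteered events separately, and the number of women who did not answer. The last column matters because women who miss D3 or D4 may include some who were hurt.
- **Non-responders.** Report how many had an injury or illness in weeks 6-8. Any Aim 1 analysis without them should be labelled exploratory, with intent-to-treat kept as primary.
- **Reconcile** the number of personal calls between Section VII and the D2 visit text.

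Cost: an estimated two minutes per questionnaire, some staff time to review positive answers, and one table. The main weakness is recall over up to about 25 weeks before D3, which the same items cannot remove but which would apply to all arms alike.
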